7.9.6. Complete Remission Duration

CR duration is defined only for patients who achieve a CR during the study and is measured from the date of CR (Day 1) until relapse.

An additional rule for defining CR duration is:

- A patient found to have relapsed after missing one or more scheduled response assessments will have his CR duration end on the scheduled date for the first missed response assessment following the last confirmation of CR

Rules for censoring CR duration are:

- A patient who dies while in remission will have his CR duration censored on the date of death
- A patient in remission on the date he is lost to follow-up will have his CR duration censored on the date of his last response assessment
- A patient in remission on the database lock will have his CR duration censored on the date of his last response assessment

Hypothesis testing for CR duration will be based on the stratified log rank test statistic (see Table 6). Stratification levels will be the same as those used for the randomization scheme (see section 6). Two Cox PH models will be fit to provide estimates of the HR. One model will include treatment arm as the only independent variable, and the second

model will include treatment arm and the stratification factors used for randomization. KM “survival” curves will be graphed for visual inspection of differences in CR duration between the treatment arms. Within–treatment-arm statistics will include the number and percentage of patients who achieve a CR, the number and percentage of censored CR durations, quartile CR durations, 95% CIs for the quartile CR durations, and KM “survival” percentages with 95% CIs at select milestone times (e.g., 6, 12 and 18 months). Between–treatment-arm statistics will include HRs from the Cox PH models and their 95% CIs.

Sensitivity analyses will be run with CR duration censored on the date of BM or PBSC transplant.

If the test for between–treatment-arm homogeneity of any baseline characteristic gives two-sided p-value <0.10, then the effect that baseline characteristic has on CR duration will be quantified using Cox PH modeling. Two PH models will be fit. One model will include the baseline characteristic in question as the only independent variable, and the second model will include the baseline characteristic and the stratification factors used for randomization.

Two endpoints analogous to CR duration will be analyzed using similar methods.

- Combined CR Duration (defined only for patients who achieve a combined CR during the study): time from the earliest date of combined CR (Day 1) until relapse after combined CR
- Combined Remission Duration (defined only for patients who achieve combined remission during the study): time from the earliest date of combined remission (Day 1) until relapse after combined remission

Response categories included in “combined CR” and “combined remission” are delineated in Section 3.

7.9.7. ECOG Performance Status

ECOG performance status will be summarized within treatment arm using shift tables.

7.10. Biomarker

The biomarker in this study is MCL-1 dependence measured by mitochondrial sensitivity to NOXA BH3 peptides. Relevant data supporting analyses of MCL-1 dependence will be listed by patient within treatment arm. Summary of baseline biomarker values will include within– and between–treatment-arm descriptive statistics appropriate for continuous variables (see section 7.7). An LR model will be fit to examine the relationship between baseline MCL-1 dependence and the independent binary variable cycle-1 CR for relapsed and refractory AML patients receiving ACM. In addition, area under the curve (AUC) will be calculated (by treatment arm) for the trapezoidal receiver operating characteristic (ROC) curve. This value will quantify the ability of MCL-1 dependence to predict cycle-1 CR.¹¹ Ninety-five percent CIs will be calculated by assuming estimated AUC follows a normal distribution.

$$\widehat{AUC} \pm z_{1-\alpha/2} SE_{AUC}$$

where the standard error SE_{AUC} is calculated by the jackknife method.¹² Data from relapsed/refractory patients receiving CM in cycle 1 and patients with newly diagnosed, high-risk AML will not be used in these analyses. Similar analyses will be conducted for (1) cycle-1 combined CR and (2) cycle-1 combined remission.

Quantifying the effect of MCL-1 dependence on response rates will not infer a safety and/or efficacy benefit (or detriment) of treatment with ACM over CM. Therefore, no statistical analyses of MCL-1 dependence across treatment arms are planned other than comparing baseline values to confirm randomization created homogeneous groups with respect to prestudy values.

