2.7 Justification for Study Treatment Plan

Based on the initial data from single-arm Phase 1 and 2 studies as well as randomized Phase 2 studies, Tolero is pursuing regulatory approval for alvocidib as part of the alvocidib, cytarabine (ara-c) and mitoxantrone hydrochloride regimen or “ACM regimen” in patients with relapsed or refractory AML. As previously noted, because there is no standard care for patients with relapsed/refractory AML, the 2014 NCCN guidelines recommend that these patients enroll in a clinical study testing new drugs or new combinations of drugs. The combination of cytarabine and mitoxantrone (CM) is one of the regimens that can be considered for these patients.

NOXA binds and deactivates MCL-1. Early studies have shown that MCL-1 dependence can predict the clinical activity of alvocidib in AML patient samples and suggests an important role for MCL-1 activity in predicting alvocidib activity. As such, Tolero is conducting this Phase 2 study to test the ability of MCL-1 activity to predict which patients will respond favorably to alvocidib treatment when administered as a bolus along with cytarabine and mitoxantrone.

While both the bolus as well as hybrid dosing regimens of FLAM have shown substantial activity in patients with AML, the hybrid regimen will be used in this study. Clinical data from a randomized study that compared the two dosing regimens suggest that the hybrid schedule tends to produce a higher remission rate (62% versus 74%) in poor-risk, newly diagnosed AML patients [17].

We have also observed a high CR rate (39%) with the hybrid regimen in relapsed and refractory AML patients (and 92% CR among relapsed-only patients) [10]. In addition, the safety profile of the two regimens appears similar, though there may be a trend to lower early mortality with the hybrid regimen. In these two studies, the incidence of Tumor Lysis Syndrome (TLS) was 9%, and treatment-related mortality was 8% and 9%, respectively.

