11.4.3 Pharmacodynamic Endpoint Analyses

Summary of baseline biomarker values will include within- and between-treatment-arm descriptive statistics. A logistic regression model will be fit to examine the relationship between baseline MCL-1 dependence and the independent binary variable achievement of CR during the study. The full model will include effects for baseline MCL-1 dependence, treatment arm, and the two-way interaction between baseline MCL-1 dependence and treatment arm. In addition, area under the curve (AUC) and 95% CI will be calculated (by treatment

arm) for the trapezoidal receiver operating characteristic curve. This value will quantify the ability of MCL-1 dependence to predict CR.

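### SAP 7.10 asks for an MCL-1 AUC by treatment arm but bars the CM arm's data, and so matches neither protocol 11.4.3 nor SAP 7.9.1

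*SAP*

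**What the plan says.** SAP 7.10 contains four statements that bear on this point.

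- The logistic model relates baseline MCL-1 dependence to "cycle-1 CR for relapsed and refractory AML patients receiving ACM". It has no arm term and no interaction.
- For the ROC analysis, "area under the curve (AUC) will be calculated (by treatment arm) for the trapezoidal receiver operating characteristic (ROC) curve".
- The exclusion follows: "Data from relapsed/refractory patients receiving CM in cycle 1 and patients with newly diagnosed, high-risk AML will not be used in these analyses".
- The section closes by saying that "no statistical analyses of MCL-1 dependence across treatment arms are planned other than comparing baseline values".

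Protocol 11.4.3 plans something different: "The full model will include effects for baseline MCL-1 dependence, treatment arm, and the two-way interaction between baseline MCL-1 dependence and treatment arm". It continues: "In addition, area under the curve (AUC) and 95% CI will be calculated", again by treatment arm. Its outcome is CR at any time during the study, whereas SAP 7.10 uses cycle-1 CR.

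SAP 7.9.1 fits cycle-1 CR on MCL-1 dependence, arm and their interaction, with a Wald test read against 0.10 and CR rates plotted within each arm by MCL-1 decile. Table 5 lists logistic regression as supportive.

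Protocol 2.7 says the study is meant to "test the ability of MCL-1 activity to predict which patients will respond favorably to alvocidib treatment".

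**The concern.** Within 7.10, a programmer cannot meet both the by-arm instruction and the exclusion. Across documents, the model in 7.10 is not the one in protocol 11.4.3, and the closing sentence of 7.10 sits against the interaction model in 7.9.1. Once results are known, either section could be cited as the plan.

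The substance matters because both arms receive cytarabine and mitoxantrone. An association between MCL-1 and CR among ACM patients could mean that MCL-1 marks benefit from alvocidib, or that it marks response to the shared chemotherapy. Only a comparison with CM patients bears on which it is. Stage 1 and the exploratory arms gave ACM to everyone, so the randomised Stage 2 CM arm is the only source of that comparison.

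**Working it through.** **1. The texts side by side**

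| | Logistic model | Arms used | AUC |
|---|---|---|---|
| Protocol 11.4.3 | MCL-1, arm, interaction | ACM and CM | by arm, with 95% CI |
| SAP 7.9.1 | MCL-1, arm, interaction | ACM and CM | none |
| SAP 7.10 | MCL-1 only | ACM only | by arm, but CM data barred |

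No section of the SAP yields a CM-arm AUC. The interaction model survives in 7.9.1, but as a step before reading the treatment term: if the interaction p-value exceeds 0.10, the arm effect is interpreted. 7.9.1 gives no rule for a p-value of 0.10 or less, which is the result that would suggest a predictive marker.

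**2. How many CM patients the exclusion covers**

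The point rests on no sample-size figure, but the two arm sizes set the scale, and both reproduce.

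- Protocol 11.2.2 (70% vs 30%, one-sided 2.5%, 90% power), unpooled variance: n = (1.960 + 1.282)² × (0.21 + 0.21) / 0.40² = 27.6, so 28 per arm.
- SAP 5.1.2 (70% vs 40%): the fixed design gives (1.960 + 1.282)² × (0.21 + 0.24) / 0.30² = 52.5 per arm. With the O'Brien-Fleming look at 56 of 106 patients, 53 per arm has 90.0% power, and the boundary p-values are 0.00321 and 0.02378 as printed.

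The exclusion therefore removes 28 or 53 CM patients from the 7.10 analyses.

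**3. Precision of an AUC in one arm**

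If MCL-1 is unrelated to CR, SE = √[(n₁ + n₀ + 1) / (12 n₁ n₀)], with n₁ patients in CR and n₀ not.

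- 28 per arm, 70/30 or 30/70 split: √[29 / (12 × 8.4 × 19.6)] = 0.12.
- 53 per arm, ACM at 70%: √[54 / (12 × 37.1 × 15.9)] = 0.087.
- 53 per arm, CM at 40%: √[54 / (12 × 21.2 × 31.8)] = 0.082.

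For a true AUC A between 0.6 and 0.8, the Hanley-McNeil formula is SE² = [A(1−A) + (n₁−1)(a−A²) + (n₀−1)(b−A²)] / (n₁n₀), with a = A/(2−A) and b = 2A²/(1+A). For CM at 28 patients (8 in CR, 20 not) and A = 0.7, SE² = (0.210 + 0.339 + 1.643)/160 = 0.0137, so SE = 0.117 and the 95% half-width is 0.23. Over A = 0.6 to 0.8 the CM half-width is 0.20 to 0.24 at 28 patients and 0.13 to 0.16 at 53.

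**4. What the ACM-only fit can and cannot show**

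The documents give no MCL-1 distribution and no slope, so these are assumptions: MCL-1 standard normal, odds ratios per SD as shown, 2,000 simulated trials per scenario, CR rates from the respective sample-size sections.

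| Scenario | ACM-only median OR (28 / 53 per arm) | Two-arm interaction p < 0.10 (28 / 53 per arm) |
|---|---|---|
| Prognostic, OR 2 in both arms | 2.16 / 2.03 | 9% / 9% |
| Predictive, OR 2 in ACM only | 2.10 / 2.06 | 29% / 48% |
| Predictive, OR 3 in ACM only | 3.34 / 3.13 | 47% / 75% |

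The first two rows are indistinguishable in an ACM-only fit. The two-arm model can tell them apart, though with limited power.

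**The case against.** **The contrast is planned elsewhere.** SAP 7.9.1 keeps CM patients in the interaction model, with a test and by-arm plots. This stands. A reader might infer from 7.10 that the CM data are discarded and that no contrast between arms remains; the SAP read as a whole does not support that.

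**The ACM-only scope is deliberate.** SAP objective 3 concerns response to ACM, SAP 7.1 repeats the exclusion, and protocol 11.3 describes the biomarker question in the same terms. The sentence in protocol 2.7 goes on to mention the other two drugs, so it can be read as response to the regimen. No listed objective asks for predictive versus prognostic value, and no biomarker analysis is in either testing hierarchy. This justifies keeping an ACM-only analysis. It does not make a by-arm AUC possible without CM data, nor explain the difference from 11.4.3.

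**Low MCL-1 values exist only under ACM.** The exploratory arms cover 0% to below 40%, while CM patients exist only above the Stage 2 cutoff. Keeping CM out of a full-range model is defensible. This stands, and it is why the two-arm model should not displace the ACM-only model.

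**Version lag.** The SAP is written to Amendment 7 and says later amendments will be reviewed; the protocol supplied describes Amendment 11. The Amendment 7 text of 11.4.3 is not available, so this may explain part of the mismatch with the protocol. It does not explain the conflict inside 7.10.

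**The closing sentence is ambiguous.** It could mean only that MCL-1 itself will not be compared between arms as an outcome, in which case it does not conflict with 7.9.1. That reading is possible, and the wording should settle it.

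**Conclusion.** The point holds as a defect of specification in 7.10. The by-arm AUC cannot be carried out as written. The section departs from the supplied protocol 11.4.3, and its closing sentence is at best unclear beside 7.9.1. The losses are the CM-arm AUC and a clear statement of which model is the biomarker analysis. Taken alone, the 7.10 analyses cannot separate predictive from prognostic value.

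A reader might go further and conclude that the trial cannot address that question at all. The documents do not support this, because the interaction test in 7.9.1 remains. Nor do they show a knowing departure from the protocol, given the gap between amendments. The primary comparison of CR rates is unaffected.

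Correction would improve the answer without making it decisive. Under the assumed slopes, interaction power at the 0.10 level is 29% to 47% at 28 per arm and 48% to 75% at 53. The contrast also covers only MCL-1 values above the eligibility cutoff, which is 30% in the protocol and 40% in the SAP.

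**What to change.** Revise SAP 7.10 as follows.

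- Limit the CM exclusion to the pooled ACM-only analysis, and keep that model, across the full MCL-1 range, as a separate analysis.
- For randomised Stage 2 patients, name the interaction model of SAP 7.9.1 and protocol 11.4.3 as a biomarker analysis, and report the interaction estimate with its CI whatever the p-value.
- Use cycle-1 CR as the outcome and align protocol 11.4.3 to it. CR at any time during the study is confounded by crossover from CM to ACM, a problem that SAP 7.9.1 already recognises for best response.
- Report the AUC with 95% CI for ACM and for CM.
- Delete the closing sentence on analyses across arms, or limit it to comparisons of MCL-1 values themselves.
- Check the section against the current protocol amendment.

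The cost is SAP wording, one line in protocol 11.4.3 and a few added outputs. MCL-1 is already measured at prescreening and cycle-1 response is already assessed, so no new data are needed. The report should state the modest precision and the truncated MCL-1 range beside the results.

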7.11. Safety Endpoints

Summaries of safety endpoints will include data collected from the safety patient population. Relevant data supporting safety analyses will be listed by patient within treatment arm.

7.11.1. 30- and 60-Day Mortality

Estimates of 30- and 60-day mortality and their pointwise 95% CIs will be derived from KM curves for OS by treatment arm (see section 7.9.4).

7.11.2. Adverse Events

Reported adverse event (AE) terms will be mapped to MedDRA preferred terminology. AEs suggestive of tumor lysis syndrome (TLS) will be flagged based in the standardized MedDRA query (SMQ) for TLS. All reported events will appear in AE listings, however only treatment-emergent adverse events will be summarized. A treatment-emergent adverse event (TEAE) is an AE that starts or increases in severity any time after the first administration of any study drug up to 30 days following the last administration of any study drug. AE severity was rated by the investigator according to Common Terminology Criteria for Adverse Events (CTCAE) version 4.03 criteria.¹³

A high-level safety summary will display the numbers of patients within each treatment arm and overall who experience one or more AEs in each of the following categories:

- All TEAEs regardless of severity or presumed relationship to study drug
- TEAEs judged related to study drug
- All TLS SMQ TEAEs
- TLS SMQ TEAEs judged related to study drug
- Treatment-emergent serious adverse events (SAEs)
- TEAEs leading to a delay in the administration of study drug
- TEAEs leading to a reduction in the protocol-specified dose of study drug
- TEAEs leading to discontinuation of study drug
- TEAEs leading to withdrawal from the study
- TEAEs leading to death

The base summary of TEAEs will show within- and between-treatment-arm incidence rates for each MedDRA primary SOC and/or PT by highest reported CTCAE severity grade and overall. A separate summary will be produced each of the AE subsets listed above. Additional AE summaries may be produced using safety data from subsets of patients and/or characterized using additional SMQs.

Partial start and end dates for adverse events will be replaced by calendar dates that maximize the duration of the adverse event. The following steps will be followed.

For a partial start date:

1. Replace a missing month with January
2. Replace a missing calendar day with the first of the month
3. If the replacement date is prior to the first dose of study drug, then set the adverse event start date equal to the date of the first dose

For a partial end date:

1. Replace a missing month with December
2. Replace a missing calendar day with the last day of the month

The replacement date for a missing end date may exceed end of the adverse event reporting period specified in the study protocol.

An end date will not be estimated for adverse events marked continuing at the end of the study.

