4.5.3 Treatment Schema

4.5.3.1 Stage 1: Treatment with ACM over Days 1-9

Patients enrolled in Stage 1 will receive treatment with ACM as outlined below:

- **Days 1, 2 and 3: alvocidib (A) - Administer Daily**
30 mg/m² as a 30-minute (± 10 minutes) intravenous (IV) bolus
followed by
60 mg/m² over 4 hours (± 15 minutes) as an IV infusion
- **Days 4 and 5: Rest (no chemotherapy treatment)**
- **Days 6, 7, and 8: cytarabine (C) - Continuous over 72 hours**
2 gm/m² by continuous IV infusion over 72 hours (± 2.5 hours)
(ie, 667 mg/m² daily for total of 2 gm/m²)
- **Day 9: mitoxantrone hydrochloride (M) is administered 12 hours after completion of cytarabine treatment**
40 mg/m² by IV infusion over 1-2 hours (± 10 minutes)

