4.5.3.2 Stage 2: Treatment with ACM or CM

Patients enrolled in Stage 2 will be randomized to either ACM or CM and will receive treatment as outlined below:

Stage 2: Randomized to ACM: Treatment with ACM over Days 1-9

Follow the Stage 1 treatment schema above

Stage 2: Randomized to CM: Treatment with CM over Days 1-4

- **Days 1, 2, and 3: cytarabine (C) - Continuous over 72 hours**
2 gm/m² by continuous IV infusion over 72 hours (± 2.5 hours)
(ie, 667 mg/m² daily for total of 2 gm/m²)
- **Day 4: mitoxantrone hydrochloride (M) is administered 12 hours after completion of cytarabine treatment**
40 mg/m² by IV infusion over 1-2 hours (± 10 minutes)

4.5.3.3 Evaluation After Cycle 1

- Patients who achieve CR, CRi, CRp, or PR after the first cycle (completion of all doses) may receive up to 3 additional optional cycles of treatment.
 - After completing the first cycle of treatment, continued use of mitoxantrone is optional.
 - Mitoxantrone must be omitted from subsequent cycles if the patient's lifetime daunorubicin equivalent exceeds 460 mg/m² (see *Appendix G* for conversion table) or the left ventricular ejection fraction (LVEF) drops below 45%.
- Patients not demonstrating evidence of CR, CRi, CRp, or PR after the first cycle of treatment will be considered for removal from the study, although with permission of the Medical Monitor, induction treatment may continue if clinically indicated and provided there is no evidence of toxicity \geq NCI CTCAE grade 4.
- Perform the End of Study Assessments for those patients who do not continue on study to receive at least one additional cycle of treatment (see *Section 5.5*).

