8.3 Serious Adverse Events

A serious adverse event (SAE) is defined as any experience that suggests a significant hazard, contraindication, side effect, or precaution. An SAE includes:

- Any death, or
- Any life-threatening event (ie, the patient is at immediate risk of death from the event as it occurred), or
- Any event that is persistently, significantly, severely or permanently disabling, or requires intervention to prevent such disability, or
- Any event which requires inpatient hospitalization or prolongs hospitalization, or
- Any congenital abnormality/birth defect, or
- Any medically significant event that may jeopardize the patient or may require intervention to prevent one of the other outcomes listed above.

In addition, any adverse event which results in termination of the patient from study will be considered a potentially serious adverse event and must be reported to the Sponsor as described in Section 8.4 below.

Bone marrow suppression and associated complications are expected events during leukemia therapy and are part of the treatment process (marrow emptying of leukemic cells). Therefore, myelosuppression and associated complications directly related to the myelosuppression, such as fever, infections and bleeding, will not be reported as serious adverse events (SAEs), but will be reported as adverse events on the adverse event CRF and will be summarized in the updated and final reports. Anemia and thrombocytopenia will not be reported as an SAE. Prolonged bone marrow suppression (as defined by the NCI toxicity criteria specific for leukemia, ie, bone marrow cellularity <5% on day 42 or later (6 weeks) from start of therapy without evidence of leukemia) or the unexpected nature, severity or frequency of myelosuppression, anemia, and thrombocytopenia or an associated complication will be reported as an SAE.

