8.5 Serious Adverse Events and/or Adverse Events Requiring Discontinuation of Study Drug

Any serious adverse event (SAE) that occurs during this study and up to 30 days after discontinuation of study drug (alvocidib in Stage 1; alvocidib, cytarabine or mitoxantrone in Stage 2) or initiation of alternate cancer therapy, whichever occurs first, must be reported to the Study Medical Monitor within 24 hours of the Investigator's awareness of the event, whether or not this reaction is considered to be associated with use of the investigational drug.

In addition, the occurrence of any AE leading to permanent discontinuation of study drug must also be reported to the Sponsor within 24 hours of the Investigator's awareness of the event.

Serious adverse events must be scanned and emailed to the Sponsor/Study Medical Monitor.

Email: [REDACTED]

It is expected that the Investigator will provide or arrange appropriate supportive care for the study patient. A patient experiencing an SAE(s) should be followed clinically until the event is resolved, deemed stable or permanent by the PI, or the patient begins a new treatment for their disease. All telephone and scanned/emailed reports must be followed with a written SAE report form within 24 hours of the Investigator's awareness of serious adverse events and nonserious events which required discontinuation of study drug.

The SAE report form should be completed and signed by the Investigator, scanned, and sent by email to the Sponsor as described above. The SAE Report Form is distinct and separate from the adverse event form included in the CRF.

Grades for all SAEs and AEs, regardless of whether they trigger expedited reporting or not, must still be captured by the CRF.

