11.4.4 Safety Analyses

The following safety analyses will be performed on all patients who receive at least one dose of study drug.

- **30- and 60-day Mortality** = Estimates of 30- and 60-day mortality and their pointwise 95% CIs will be derived from Kaplan-Meier curves for OS by treatment arm
- **Adverse Events** = Reported AE terms will be mapped to MedDRA preferred terminology. All reported events will appear in AE listings, however only TEAEs will be summarized. A TEAE is an AE that starts or increases in severity any time after the first administration of any study drug up to 30 days following the last administration of any study drug. AE severity will be rated by the investigator according to NCI CTCAE version 4.03 in Stage 1 and version 5.0 in Stage 2 (see *Appendix C*).
- **Clinical Laboratory Assessments** = Laboratory test results measured on a continuous scale and changes from baseline values will be summarized by visit and within treatment arm using mean, standard deviation, median, minimum and maximum values. Categorical test results will be summarized within treatment arm using shift tables. Additionally, for tests where NCI CTCAE, version 4.03 in Stage 1 and version 5.0 in Stage 2 (see *Appendix C*), severity criteria are specified, NCI CTCAE severity grades will be summarized in shift tables.
- **Vital Signs** = Vital signs and changes from baseline values will be summarized by visit and within treatment arm using mean, standard deviation, median, minimum and maximum values.

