7.9.2. Progression-Free Survival

PFS time is defined for all patients and is measured from the date of randomization (Day 1) until (a) treatment failure, (b) relapse after combined remission, or (c) death from any cause, whichever occurs first.

Treatment failure is defined as failing to achieve a combined remission following induction therapy. The date of treatment failure is the protocol-specified date for bone marrow collection following the first induction attempt (i.e., at neutrophil and platelet recovery or Day 45 of the treatment cycle, whichever occurs first), regardless of whether the patient received a second induction attempt (unless the second induction resulted in a combined remission in which case “treatment failure” does not apply).

Additional rules for defining PFS time are:

- A patient found to have relapsed after missing one or more scheduled response assessments will have his PFS time end on the scheduled date for the first missed response assessment following the last confirmation of combined remission
- A patient who misses the first scheduled response assessment and who never achieves combined remission will have his PFS time end on the scheduled date for the first response assessment (unless the patient died before this date)

Rules for censoring PFS time are:

- A patient with PFS continuing as of the date he is lost to follow-up will have his PFS time censored on the date of his last response assessment
- A patient with PFS continuing as of the database lock will have his PFS time censored on the date of his last response assessment

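### Prolonged marrow suppression, an SAE only from Day 42, can fall after the 30-day TEAE window in one-cycle patients and then be listed but not counted in the AE and SAE summaries

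*SAP*

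**What the plan says.** **Counting rule.** SAP 7.11.2 states: "All reported events will appear in AE listings, however only treatment-emergent adverse events will be summarized". Protocol 11.4.4 uses the same definition: "A TEAE is an AE that starts or increases in severity any time after the first administration of any study drug", with the period running "up to 30 days following the last administration of any study drug". SAP section 3 counts all three drugs as study drug.

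**The event.** Protocol 8.3 takes ordinary myelosuppression out of SAE reporting and sends it to the adverse event form. It keeps prolonged marrow suppression as an SAE, defined as "bone marrow cellularity <5% on day 42 or later (6 weeks) from start of therapy without evidence of leukemia". It also keeps myelosuppression of unexpected nature, severity or frequency.

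**Last doses.** Protocol 4.5.3.1 for ACM: "Day 9: mitoxantrone hydrochloride (M) is administered 12 hours after completion of cytarabine treatment". Protocol 4.5.3.2 for CM: "Day 4: mitoxantrone hydrochloride (M) is administered 12 hours after completion of cytarabine treatment".

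**When the marrow is taken.** SAP 7.9.2 gives the timing as "at neutrophil and platelet recovery or Day 45 of the treatment cycle, whichever occurs first". Protocol 5.4.4 allows ±2 days and requires a non-diagnostic sample to be repeated within 7 days.

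**SAE reporting.** Protocol 8.5 covers SAEs during the study and "up to 30 days after discontinuation of study drug", or until other cancer therapy starts if that is earlier.

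**The concern.** The protocol makes a specific point of keeping this event as an SAE, but its defining date lies beyond the period in which events are counted for a patient who receives one cycle. Neither document has an exception that brings it into the summaries, and neither says which onset date applies.

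At stake is the between-arm safety comparison. ACM is CM plus a third drug, so a reader will look in the AE and SAE tables for a difference in prolonged aplasia. As written, those tables could show few or none of these events for reasons unrelated to how often they occur. The count would depend on how each site dates onset and on whether the patient went on to further study drug.

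**Working it through.** The check is calendar arithmetic.

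**Inputs**
- Qualifying day: Day 42 (protocol 8.3). The protocol also gives this as 6 weeks: 6 × 7 = 42, so its two figures agree.
- Last dosing day of one on-schedule cycle: Day 9 for ACM, Day 4 for CM (protocol 4.5.3.1 and 4.5.3.2).
- TEAE window: last dose + 30 days (SAP 7.11.2, protocol 11.4.4).
- Marrow without count recovery: Day 45 ±2, that is Day 43 to Day 47. A repeat within 7 days can fall as late as 47 + 7 = Day 54.

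**Results**

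| | ACM | CM |
|---|---|---|
| Window closes | 9 + 30 = Day 39 | 4 + 30 = Day 34 |
| Gap to Day 42 | 42 − 39 = 3 days | 42 − 34 = 8 days |
| Gap to earliest scheduled marrow (Day 43) | 43 − 39 = 4 days | 43 − 34 = 9 days |
| Gap to latest scheduled marrow (Day 47) | 47 − 39 = 8 days | 47 − 34 = 13 days |
| Gap to latest repeat marrow (Day 54) | 54 − 39 = 15 days | 54 − 34 = 20 days |
| Slip in last dose that brings Day 42 inside | 42 − 30 − 9 = 3 days | 42 − 30 − 4 = 8 days |

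**Routes by which the event could still be counted**
1. *A later cycle or crossover.* The window runs continuously from first dose to 30 days after the last dose ever given, so more study drug brings the Day 42 event inside. Protocol 4.5.3.3 lets non-responders continue only with the Medical Monitor's permission and without grade 4 or higher toxicity. Protocol 4.5.3.4 offers crossover on the CM arm only. This route is therefore not equally open to both arms.
2. *An earlier onset date.* Protocol 8.4 asks sites to record the start and stop of the whole event, not of its worst-grade portion. A site that treats prolonged suppression as one continuous event from the first cytopenia would give an in-window start. A site that treats the Day 42 finding as a new event would not. Reaching the threshold for seriousness is not in itself an increase in severity, so the worsening clause does not settle the matter.
3. *Other summaries.* SAP 7.11.4 summarises Cycle 1 laboratory results until Cycle 2 starts or to 10 weeks (about Day 70). Its weekly points include Day 43 in both arms: 15 + 4 × 7 for ACM and 8 + 5 × 7 for CM. The haematology panel in protocol Appendix D is blood counts only. The 8.3 event needs low cellularity without leukaemia, and counts cannot separate that from cytopenia caused by persistent disease. SAP Table 1 lists time to neutrophil and to platelet recovery as safety endpoints, but section 7.11 gives no method for them and Table 9 has no row.

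**SAE reporting window.** Counted the same way, the 30 days in protocol 8.5 also end on Day 39 or Day 34 in Stage 2. In Stage 1 they are counted from alvocidib, whose last dose is on Day 3, so they end on 3 + 30 = Day 33. All three fall before Day 42.

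**The case against.** The strongest reply is that Day 42 is a threshold for seriousness and not an onset rule. Prolonged suppression continues the myelosuppression that chemotherapy causes from the start, protocol 8.3 already has that recorded as an adverse event and summarised, and the dating convention in 8.4 would place the start inside the window. This stands as a possible reading. It does not remove the problem, because nothing says that the 8.3 event takes the earlier date, so two sites could date the same case differently.

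Several stronger readings are tempting, and the documents do not support them:
- *That the event is missing from every safety summary, or is never captured.* It appears in the listings, related blood counts are summarised to 10 weeks, and an earlier onset date, a late last dose or a further cycle would bring it in. The Table 9 titles for the SAE tables also lack the treatment-emergent label that neighbouring tables carry. SAP 7.11.2 restricts summaries to TEAEs and lists treatment-emergent SAEs, so this is an ambiguity to resolve and not proof of either reading.
- *That the CM window is defective because it closes 5 days earlier.* Both arms get the same 30 days after the last dose. ACM takes 5 days longer to give.
- *That delayed marrow recovery is the toxicity most likely to differ between arms.* No passage establishes this.
- *That the data are lost.* AEs are assessed at the response visit (protocol 5.4.4). Protocol 8.3 requires the event to be reported as an SAE, and 8.5 also covers events during the study. The 8.3 and 8.5 wording conflicts, but that does not show that cases would go unreported.

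**Conclusion.** The concern holds in conditional form. If onset is dated to the qualifying marrow, and the patient received one on-schedule cycle and no later study drug, the 8.3 event lies at least 3 days (ACM) or 8 days (CM) outside the TEAE window. SAP 7.11.2 then lists it without counting it in the TEAE and treatment-emergent SAE summaries. If onset is dated to the first myelosuppression, it is counted. The documents do not choose between the two, so the tabulated rate would reflect site practice and subsequent treatment as well as incidence.

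The documents give no expected frequency for this event, so the number of patients affected cannot be estimated. Efficacy analyses are not touched. The point should be corrected before the safety tables are produced.

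**What to change.** Keep the 30-day TEAE window. In SAP 7.11.2 and protocol 11.4.4, add that prolonged marrow suppression as defined in protocol 8.3 is summarised by arm whatever its onset date. State which arm a crossover patient counts under: for the safety population, protocol 11.3 assigns a patient to ACM once alvocidib is given at any time, whereas SAP 7.1 excepts crossover patients.

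Also reconcile:
- the SAE reporting window in protocol 8.5 with the Day 42 definition in 8.3;
- the SAE table titles in SAP Table 9 with the TEAE-only rule in 7.11.2.

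Extending the TEAE window to the response marrow is less clean, because its length would depend on outcome. An ACM patient who recovers on Day 30 would be observed to Day 39, while one who has not recovered would be observed to Day 47, or Day 54 with a repeat marrow. All adverse events would then be collected for longer in the slower-recovering patients.

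The cost is wording in both documents and slightly more events tabulated. No new visit is needed, since AEs are already assessed at the response marrow.
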